6.2 ENDPOINT AND OTHER NON-SAFETY ASSESSMENTS

The primary outcome will be measured from hospital electronic record (EMR), billing data and/or from the Get With the Guidelines (GWTG) stroke registry data. Data will be separately received from the three hospitals in Flint where patients are sent for EVT (received letters of support and UFA in progress), which together account for 95% of all stroke treatments in Flint residents. The study population will be patients with a primary diagnosis of ischemic stroke using ICD-9 codes and/ or ICD-10 codes^{33, 34}. The primary outcome will be any thrombolysis which includes both IV tPA (MS-DRG 61-63 or ICD-9 procedure code 99.10), intra-artery treatment (MS-DRG 21-23 or CPT codes 37184-6, 37201, 75896) and the combination identified by ICD-9 and ICD-10 codes.³ The research team will attempt to obtain data from 2010 to 2021 if available to account for linear trends (about 6000 ischemic stroke and 8000 total strokes and TIAs). Data will also be obtained from the de-identified publicly available Michigan State Inpatient Database for stroke rates in comparator cities.

Secondary Outcomes: The community secondary outcomes are the number of stroke patients who arrive by ambulance and IV acute stroke treatment rates. Data will be obtained from the EMR. We also request data from the State of Michigan, specifically Michigan Department of Health and Human Services, Michigan EMS Information System UFA (21-UFA04001) or GWTG data of the three hospitals in Flint.

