7.1.1 ANALYSIS OF THE PRIMARY ENDPOINT(S)

The primary analysis will be an interrupted time series comparison of acute stroke treatment rates in the three Flint hospitals. The pre-intervention period will be defined using EMR data prior to the start of the roll out of the community intervention. All patients admitted with a primary diagnosis of ischemic stroke in both the pre-intervention and intervention periods will be included in the primary analysis. Note: process measures evaluating the Stroke Ready campaign (quadrant crossover or music video view IP address) will not be linked to any obtained PHI. Logistic regression will be used to estimate the overall intervention efficacy (indicator variable) in a model predicting receipt of acute stroke treatment (binary variable). If a temporal trend exists in the pre-intervention period, we will adjust for the month since the start of the pre-period as a fixed effect while accounting for clustering at the hospital level. To maximize statistical power, both interventions (hospital-HUM00112536 and all community quadrants-this current protocol) will be parameterized with a single variable. With this approach, statistical power for the primary analysis will be more than adequate. Using hospital administrative and Medicare data, we estimate that at least 480 strokes per year will occur at the 3 Flint hospitals for a total of at least 1,440 strokes in the pre period and 1,800 in the post-period, but to be conservative we are requesting data from 2010 to 2021 about 8000 patients with a stroke. Assuming a doubling in treatment rates (pre-intervention Medicare treatment rate 2.2%),³⁷ we will have over 90% power to detect this difference considering a two-sample binomial difference in proportions. This estimate is consistent with prior simulation work based on ARIMA analyses (effect size of 1.0 (pre-intervention monthly treatment rate = 2.2%, standard deviation = 2.1, predicted post-intervention treatment rate 4.3%, auto-correlation=0.3).³⁸

7.1.2 SECONDARY ANALYSES: REGIONAL COMPARISONS AND QUADRANT-BASED ANALYSES TO ENHANCE CAUSAL INFERENCE

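### Calendar month enters the primary model only on an undefined trend condition, so a missed secular rise in treatment can be credited to the intervention

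*Combined protocol and SAP*

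**What the plan says.** Section 7.1.1 of the combined protocol and SAP names an interrupted time series and then describes a patient-level model with one pre/post term: "Logistic regression will be used to estimate the overall intervention efficacy (indicator variable"). Calendar time is conditional: "If a temporal trend exists in the pre-intervention period, we will adjust for the month since the start of the pre-period". The section does not say how the existence of a trend will be judged.

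The pre-period has two versions. For power, the section takes 480 strokes a year across the three hospitals as a minimum and states the totals as follows: "for a total of at least 1,440 strokes in the pre period and 1,800 in the post-period". It then adds that "to be conservative we are requesting data from 2010 to 2021 about 8000 patients with a stroke". Section 6.2 gives the reason for the longer series and its uncertainty: "The research team will attempt to obtain data from 2010 to 2021 if available to account for linear trends". Section 6.2 also shows that about 6,000 of the roughly 8,000 cases are ischemic strokes, which is the primary population.

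The power statement of more than 90% for a doubling from 2.2% rests on a two-sample comparison of proportions, which has no time term. Section 7.1.2 plans a regional control model and a quadrant model to explore confounding. Both are secondary and both repeat the primary analysis.

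**The concern.** In a single-city series without a concurrent control, a background rise in tPA or endovascular use is the main rival explanation for any pre/post difference. A time term is what separates the two. Here its presence depends on what the pre-period appears to show, and that pre-period may hold only about 1,440 × 0.022 ≈ 32 treated patients. A trend too weak to be noticed there can still build up a sizeable pre/post gap by the end of follow-up.

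Because the criterion is undefined, the choice of primary model is also left open until the data are seen. The consequences reach beyond the primary test. The geographic model (7.1.2) inherits the rule, the hospital/community decomposition (7.1.3) builds on that model, and the cost-effectiveness analysis (7.1.5) uses the primary effect size to derive QALYs.

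**Working it through.** **Inputs from the documents.** 480 strokes per year, so 40 per month. 1,440/480 = 3 years (36 months) pre and 1,800/480 = 3.75 years (45 months) post. Pre-intervention rate 2.2%, doubling to 4.4%.

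**Assumptions.** Two-sided 5% for the primary test and for the pre-test (neither is stated). Log-linear odds growth of 1.05 to 1.20 per year. Mean pre-period rate 2.2%. For 2010–2021, roll-out in mid-2018, giving 102 pre and 42 post months; the proxy is the June 2018 start of workshop data collection in Section 8.1. No hospital clustering or autocorrelation.

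**1. The plan's own power.** Pooled rate = (1,440 × 0.022 + 1,800 × 0.044)/3,240 = 0.0342. The standard error is 0.00643 under the null and 0.00619 under the alternative. Power = Φ[(0.022 − 1.96 × 0.00643)/0.00619] = Φ(1.52) ≈ 93.6%. The stated figure reproduces, without a time term.

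**2. Gap produced by a missed trend.** The midpoints of the two periods lie (36 + 45)/2 = 40.5 months, or 3.375 years, apart. With growth g per year and no intervention effect, the unadjusted odds ratio is about g^3.375: 1.18, 1.38 and 1.60 for g = 1.05, 1.10 and 1.15. The assumed doubling is an odds ratio of 2.05. Growth of 2.05^(1/3.375) ≈ 1.24 per year would mimic it.

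**3. Chance of noticing the trend.** In a logistic model, SE(slope) ≈ 1/√[n p(1−p) Σ(x − x̄)²]. With n = 40, p = 0.022 and Σ = 26.98 years² over 36 months, SE ≈ 0.208 per year. For g = 1.10, ln(1.10)/0.208 = 0.46, so the power of the pre-test is about 7%. At g = 1.24 it is about 18%.

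**4. The two-step rule, simulated with no true effect.** Pre-period slope tested at 5%; month added only if significant. Several thousand runs per scenario; ranges span repeat simulations.

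| Odds growth per year | 36+45 months: trend detected | 36+45: false positives | 102+42 months: trend detected | 102+42: false positives |
|---|---|---|---|---|
| 1.00 | 5% | 5% | 4–5% | 6–7% |
| 1.05 | 5% | 11% | 20% | 31–33% |
| 1.10 | 6–7% | 28–31% | 57–59% | 40–42% |
| 1.15 | 9–10% | 54–57% | 87–90% | 13–15% |
| 1.20 | 13–14% | 73–75% | 98–99% | 5–7% |

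With month always in the model, false positives are 4–6% in every row. A looser pre-test (20%) on the short series still gives 12% and 24% at 1.05 and 1.10; on the long series it gives 22% and 20%. If 2.2% is taken as the starting rate rather than the pre-period mean, the short series gives up to 33% and 61% at 1.10 and 1.15, and the long series about 27% at 1.10.

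**5. Power with month always included, no secular trend.** The log odds ratio for a doubling is ln(2.046) = 0.716.
- 1,440/1,800: the standard error of the intervention term rises from 0.213 to 0.384, so its variance is multiplied by (0.384/0.213)² ≈ 3.2. Power = Φ(0.716/0.384 − 1.96) ≈ 46%; simulation gives 47–48%.
- 102+42 months at 40 per month: the standard error is 0.292. Power = Φ(0.716/0.292 − 1.96) ≈ 69%; simulation gives 69–70%.

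Reaching 90% on the 36+45 split would need about 3.0 times the strokes: 3.02 × 3,240 ≈ 9,800.

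**The case against.** A reader might infer that the rule has almost no chance of finding a trend on any data set, or that secular growth will in fact be credited to Stroke Ready. The documents support neither. The longer series is requested expressly to handle linear trends. If it arrives, the assumed pre-test finds growth of 1.15 or more in roughly nine runs out of ten, and the inflation largely disappears. The plan also states no secular growth rate, and with no growth the rule is close to nominal. The 5% pre-test is assumed too: the wording could mean inspection or a looser threshold. Finally, Section 7.1.2 openly addresses confounding through a concurrent regional control.

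These points limit the concern but do not remove it. The longer series is only to be had if available, and even then growth of 1.05 to 1.10 per year leaves false positives at about a third or more under a 5% pre-test. A looser threshold reduces the inflation without removing it. The regional model is secondary, so the primary result stands or falls without it. The absence of a defined criterion is itself a defect, because it leaves the primary model open to a data-dependent choice.

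One further objection stands. Always including month is not a complete cure. If growth of 1.10–1.15 per year began only 12 months before roll-out, the always-adjusted model on 2010–2021 would give about 9–15% false positives. That is well below the conditional rule (31–58%), but above 5%.

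**Conclusion.** The concern holds as a conditional one. Following the stated rule can give a wrong primary conclusion if treatment was rising moderately in the background. Under the assumed 5% pre-test, false positives are about 11%, 30% and 54–57% on the plan's 1,440/1,800 strokes at yearly odds growth of 1.05, 1.10 and 1.15. On 2010–2021 they are about 32%, 41%, 14% and 6% at 1.05, 1.10, 1.15 and 1.20. The growth rates, the pre-test and the mid-2018 roll-out are assumptions, and hospital clustering and autocorrelation are ignored.

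That the conditional, undefined time adjustment is at odds with the interrupted-time-series label is certain from the text. That a bias will occur is not. The stated power of over 90% applies only to the model without a time term. This needs correction before analysis because it bears on the validity of the primary test.

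**What to change.** Delete the condition in Section 7.1.1. Include calendar month in the primary logistic model whatever the pre-period shows, and carry the same rule into the analyses that repeat it (the regional and geographic models in 7.1.2 and the component model in 7.1.3).

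Fix the pre-period window in advance by reconciling the 1,440-stroke version with the 2010-onward version, counted in ischemic strokes. State what happens if the earlier years cannot be obtained.

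Restate power for the model with month: about 47% for a doubling on 1,440/1,800 and about 70% on 2010–2021, before any allowance for hospital clustering or autocorrelation. Since month restores about 5% type I error only if the secular trend is roughly log-linear, say that the regional control model will be read alongside the primary result.

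The wording change is small and needs no data beyond those already requested. The real cost is power: an estimate that separates the intervention from time is much less precise, and the plan should say so.

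### The primary logistic model has no term for serial correlation, although the plan's own power text assumes 0.3, and the method for clustering by three hospitals is left open

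*Combined protocol and SAP*

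**What the plan says.** Section 7.1.1 describes the primary analysis as an "interrupted time series comparison of acute stroke treatment rates in the three Flint hospitals". The estimate comes from a patient-level logistic regression for receipt of acute treatment, with a single indicator covering the hospital and community interventions together. The pre-period ends when the community roll-out starts.

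Time and clustering share one conditional sentence. It opens "If a temporal trend exists in the pre-intervention period, we will adjust for the month" and ends "as a fixed effect while accounting for clustering at the hospital level". No clustering method is named (fixed effects, random intercept, GEE or sandwich), no correction for few clusters is given, and there is no lagged, autoregressive or autocorrelation-robust term.

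Power of over 90% for a doubling from 2.2% rests on a two-sample binomial comparison with "at least 1,440 strokes in the pre period and 1,800 in the post-period". The plan adds: "This estimate is consistent with prior simulation work based on ARIMA analyses". The inputs to that work are a monthly standard deviation of 2.1, a post-intervention rate of 4.3% and autocorrelation of 0.3.

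No other section supplies a correction. The regional and geographic models in section 7.1.2 repeat the primary analysis, so they inherit the gap.

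**The concern.** The plan treats monthly rates as correlated when it supports its power, then specifies a model that treats patients as independent over time. The intervention contrast is purely before against after, and it switches in all three hospitals together. Positive correlation between neighbouring months therefore makes the true standard error larger than the logistic model reports. Hospital intercepts remove stable differences between hospitals but leave this dependence in place.

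The clustering clause raises a second problem. One common reading, a hospital-level sandwich or GEE standard error with a z test, performs badly with three clusters. As written, it is also unclear whether clustering is handled at all when no trend is found. The primary p-value and interval would then depend on choices that could be made after the data are seen.

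**Working it through.** **Inputs, all from section 7.1.1.** Three hospitals; "at least 480 strokes per year will occur at the 3 Flint hospitals", which is 480/12 = 40 a month; 1,440/40 = 36 pre-months and 1,800/40 = 45 post-months; rates 2.2% and 4.4%; monthly SD 2.1 points; autocorrelation 0.3. No significance level is stated, so two-sided 0.05 is assumed.

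**1. The plan's own figures reproduce.**
- Pooled rate: (1,440 × 0.022 + 1,800 × 0.044)/3,240 = 0.0342. The standard error is 0.00643 under the null and 0.00619 under the alternative. Power = Φ((0.022 − 1.96 × 0.00643)/0.00619) = Φ(1.52) = 93.6%.
- ARIMA effect size: (4.3 − 2.2)/2.1 = 1.0.

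**2. Effect of autocorrelation 0.3 on the standard error.** These are exact AR(1) variances of the level change over 36 + 45 months, in units of the monthly SD.

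| Model | Naive SE | True SE | Ratio | True error of a 5% test |
|---|---|---|---|---|
| Level only | √(1/36 + 1/45) = 0.224 | 0.301 | 1.35 | 2[1 − Φ(1.96/1.35)] ≈ 14.5% |
| With linear month | 0.439 | 0.578 | 1.31 | ≈ 13.6% |

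**3. The same on the logistic model's own scale.** That model uses binomial variance. At 2.2% and 40 strokes a month the binomial SD is √(0.022 × 0.978/40) = 2.32 points, above the plan's 2.1. The ratios become 1.35 × 2.1/2.32 ≈ 1.22 and 1.31 × 2.1/2.32 ≈ 1.19, giving errors of about 11% and 10%. At autocorrelation 0.1 the level-only ratio is 1.10, or 1.10 × 2.1/2.32 ≈ 1.00 on this scale, so the error lies between about 7.5% and 5%.

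**4. Patient-level simulation with no effect.** There were 3,000 runs per setting with three hospitals and 81 months. The hospital intercept SD of 0.3 on the logit scale is assumed.

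| Analysis | Independent patients | Shared AR(1) month effect (assumed logit SD 0.5, correlation 0.3) |
|---|---|---|
| Hospital fixed effects | about 5% | about 10% |
| Three-cluster sandwich, z test | about 26% | 32-33% |
| Sandwich × √(3/2), t on 2 df | 4.5-5.4% | about 7% |

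Further runs of the sandwich with a z test under independence, with unequal hospitals, gave 24-27%. In the right-hand column the correlation of 0.3 belongs to the underlying month effect; the observed monthly rates show only about 0.03, because binomial noise dilutes it. A far stronger assumed effect (SD 0.8, correlation 0.8) gives an observed correlation of 0.24 and errors of 37-44% with fixed effects. It implies monthly variation above the plan's 2.1, so no weight is placed on it.

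**5. Power.**
- Dividing the binomial sample by (1 + 0.3)/(1 − 0.3) = 1.857 leaves about 775 and 969 patients, and power of about 72%.
- On the ARIMA inputs with a correct standard error, a level-only contrast has Φ(1/0.301 − 1.96) ≈ 91%, which agrees with the plan. With a linear month term it has Φ(1/0.578 − 1.96) ≈ 41%.

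**The case against.** The strongest reply is that the plan leaves a gap rather than specifying a faulty method. It never names a sandwich estimator, and hospital indicators or a sandwich with t on 2 df also account for clustering and are near nominal under independence. This stands. A reader might infer that the primary analysis will have a 25% false-positive rate, but the documents do not support that: the figure belongs to one possible choice.

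A reader might also infer that three hospitals rule out a random intercept. They do not. In simulations under independence with no month term (1,000 runs per setting, likelihood-ratio test), a random intercept rejected 5.4%, 5.3% and 4.6% of the time for assumed hospital SDs of 0, 0.3 and 0.6. The contrast is within hospital, so a poorly estimated variance hardly matters. Like fixed effects, however, a random intercept leaves serial correlation unmodelled.

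Next, 0.3 is a design input, and it fits poorly with the other inputs. If correlation comes from a drifting rate on top of binomial noise, a lag-1 value of 0.3 needs a monthly SD of at least 2.32/√0.7 = 2.77, against the stated 2.1. True inflation may therefore be small. This also stands, and is why the size is given as a range.

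The two problems are partly alternatives as well. A hospital sandwich allows correlation over time within a hospital but fails with three clusters; intercepts avoid that failure but ignore time. The errors should not be added together. Finally, the condition on clustering rests on the grammar of one sentence and may not be intended.

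**Conclusion.** The concern holds in a conditional form. Under the plan's own autocorrelation of 0.3, the specified model gives standard errors that are too small. The true error of a nominal 5% test is about 10-15%: about 10-11% using the monthly SD of 2.1, and about 14% when the naive standard error is taken from the scatter of monthly rates. At 0.1 there is little or no inflation. An uncorrected three-cluster sandwich or GEE with a z test would give about 25% even with independent patients, but the plan does not commit to it.

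The power figure of over 90% is arithmetically correct for independent patients. The ARIMA check supports it for a level-only contrast with SD 2.1, but not for the trend-adjusted model that the plan may end up fitting.

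These results assume a two-sided 0.05 test, 36 + 45 months at 40 strokes a month, AR(1) dependence, and the hospital and month variances stated with the simulations.

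**What to change.** Amend section 7.1.1, and through it the models in 7.1.2, as follows.

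- Include hospital as two fixed-effect indicators in every model, whether or not a pre-period trend is found.
- Model monthly autocorrelation in the primary inference, with an AR(1) error or an equivalent model for monthly or hospital-month rates, and allow for overdispersion.
- Exclude an uncorrected three-cluster sandwich or z test. Any sandwich must carry a few-cluster correction, such as t on 2 df.
- Do not rely on uncorrected Newey-West errors with about 81 months. In simulation at autocorrelation 0.3 they still reject about 10-13% of the time, against about 7% for an AR(1) model. With a month term and no autocorrelation they reject 9-10%, against 5.6% for ordinary standard errors.
- State that the over-90% power is for independent patients, and restate power under the autocorrelated model with and without the month term.

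The cost is SAP wording and two extra coefficients. Intervals will be slightly wider and the stated power less favourable. The AR(1) model remains a little above nominal, which the plan should acknowledge.

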1 PROTOCOL SUMMARY**1.1 SYNOPSIS**

Title:	Stroke Ready: A Community Based Participatory Trial to Increase Stroke Treatment
Grant Number:	U01MD010579
Study Description:	Stroke Ready is a health behavior theory-based, multi-level intervention, designed to increase acute stroke treatment in Flint, MI. The hospital-level intervention aims to optimize acute stroke hospital care in a safety net ED. Meanwhile, the community intervention seeks to increase acute stroke treatment (by decreasing pre-hospital delay). Stroke Ready also aims to inform future stroke preparedness interventions by exploring the relative importance of hospital optimization and community interventions.
Objectives:	To increase acute stroke treatment rates in Flint, Michigan through a two-pronged approach of hospital and community level interventions. To inform future CPBR acute stroke interventions by exploring both the relative importance of community and hospital interventions.
Endpoints:	
Primary Endpoint:
 
 Acute Stroke Treatment Rates (tPA and endovascular treatment) 
Secondary Endpoints:
 
 Acute Stroke Treatment Rates (tPA) Number of emergency department arrivals by ambulance
Study Population:	Adults in the Flint Community
Description of Study Intervention/Experimental Manipulation:	Stroke Ready is a community based, health theory based, peer-delivered intervention delivered in a stepped wedge design to each of the four Flint community quadrants over the course of 2 years
Study Duration:	24 months
Participant Duration:	Single-session

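### The power of over 90% is for an unadjusted comparison of two proportions; if the planned month term enters the primary model, power for a doubling is about 46% on the stated counts and about 70% on the full 2010-2021 ischemic series

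*Combined protocol and SAP*

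**What the plan says.** Section 7.1.1 specifies an interrupted time series comparison in the three Flint hospitals. It is fitted by logistic regression of treatment receipt on one indicator that covers both the hospital and the community interventions. If a trend exists before the intervention, month since the start of the pre-period is added as a fixed effect, with clustering at hospital level accounted for. The section does not say how a trend will be judged to exist.

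The same section describes power as ample. It puts the yearly volume at no fewer than 480 strokes, gives the counts as "for a total of at least 1,440 strokes in the pre period and 1,800 in the post-period", and assumes the 2.2% treatment rate doubles. On that basis "we will have over 90% power to detect this difference considering a two-sample binomial difference in proportions". It adds that this agrees with simulation work based on ARIMA analyses: "effect size of 1.0 (pre-intervention monthly treatment rate = 2.2%, standard deviation = 2.1", with a post-intervention rate of 4.3% and autocorrelation of 0.3.

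Three other statements bear on the inputs:
- Section 1.1 gives a study duration of 24 months, with delivery "to each of the four Flint community quadrants over the course of 2 years".
- Section 6.2 seeks data for 2010 to 2021, if available, to allow for linear trends, and sizes them at "about 6000 ischemic stroke and 8000 total strokes and TIAs".
- Section 7.1.1 cites the 8,000 as a conservative reserve, but limits the analysis to a primary diagnosis of ischemic stroke.

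**The concern.** The test that was powered is not the model that was specified. In a before-after series the intervention indicator and calendar month are strongly correlated, so adding month inflates the variance of the intervention estimate. The plan provides for that term and requests a long series because of trends, yet gives no power for the model that contains it. If the term is needed, a true doubling could well be missed, and a null result would be read against a claim of over 90% power.

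**Working it through.** **Inputs.** Rates of 2.2% and 4.4%, 1,440 and 1,800 strokes, and 480 strokes per year (40 per month) come from section 7.1.1. So 1,440 strokes is 36 months and 1,800 is 45 months (1,800/480 = 3.75 years). Assumed here: two-sided alpha of 0.05 (none is stated for this calculation), no hospital clustering (no intraclass correlation is given), and roll-out from June 2018. That date is the earliest workshop data date in section 8.1; the plan gives no launch date. January 2010 to December 2021 is then 101 + 43 months.

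**1. The plan's own figure.** Pooled rate = (1,440 × 0.022 + 1,800 × 0.044)/3,240 = 0.0342. The standard error is 0.00643 under the null and 0.00619 under the alternative. Power = Φ[(0.022 − 1.96 × 0.00643)/0.00619] = Φ(1.52) = 93.6%. The stated figure reproduces.

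**2. Logistic model without month.** Log odds ratio = ln[(0.044/0.956)/(0.022/0.978)] = 0.716, an odds ratio of 2.05. Variance = 1/(1,440 × 0.022 × 0.978) + 1/(1,800 × 0.044 × 0.956) = 0.0455, so SE = 0.213. Power = Φ(0.716/0.213 − 1.96) = 92%.

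**3. Logistic model with a linear month term.** The SE comes from the inverse of X′WX, where X holds the intercept, indicator and month, and W is the monthly count × p(1 − p). Power = Φ(0.716/SE − 1.96). The odds ratio detectable with 90% power is exp[(1.96 + 1.28) × SE].

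| Series | SE without month | Power | SE with month | Power | Detectable OR with month |
|---|---|---|---|---|---|
| 36 + 45 months, 40 per month (1,440/1,800) | 0.213 | 92% | 0.384 | 46% | 3.5 |
| 36 + 24 months, 40 per month (1,440/960) | 0.239 | 85% | 0.477 | 32% | 4.7 |
| 101 + 43 months, 40 per month (5,760 in all) | 0.159 | 99% | 0.294 | 68% | 2.6 |
| 101 + 43 months, 6,000 in all (41.7 per month) | 0.156 | 99% | 0.288 | 70% | 2.5 |

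On the stated counts the variance inflation is (0.384/0.213)² ≈ 3.2. Simulation agrees: 48.5% for 36 + 45 months, 32% for 36 + 24, and 72% for 102 + 42 months at 42 strokes per month.

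**4. The ARIMA cross-check.** The effect size is (4.3 − 2.2)/2.1 = 1.0. Binomial noise alone at 40 strokes per month gives a monthly SD of √(0.022 × 0.978/40) = 2.32 points, already above 2.1. An SD of 2.1 needs 0.022 × 0.978/0.021² ≈ 49 strokes per month, whereas 6,000 ischemic strokes over 144 months is 41.7. Taking SD 2.1 and autocorrelation 0.3 at face value, generalised least squares on 36 + 45 months gives 92% for a level change alone and 43% with a trend term. The sentence states no series length, trend term or resulting power, so it cannot stand in for the model with month.

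**5. The 8,000.** If all 8,000 records were eligible, power with month would be about 82%. Section 6.2 puts the eligible ischemic strokes at about 6,000, which gives about 70%.

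**The case against.** The plan names its test openly, and the figure for that test is correct. The month term is conditional. If there is no true trend and month is added only when the pre-period slope is significant at 5% (an assumed rule), simulated power is 93% for 36 + 45 months and 84% for 36 + 24. So a reader who infers that the planned model simply delivers 32% to 70% power goes too far; those figures apply when the month term is in the model. This part of the objection stands.

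It does not rescue the claim of ample power, because the trend case is one the plan itself prepares for. The conditional rule is also weak protection on a short baseline. In a simulation with the odds of treatment rising by 50% over 36 months and no intervention effect, the slope reached 5% significance in only about 10% of runs.

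A reader might also infer from the 24-month duration that 960 post-period strokes is right and 1,800 wrong. The documents do not show that. The 24 months match the delivery schedule, while outcome data run to 2021 (sections 3 and 6.2), materials stay in each quadrant afterwards (sections 4.2 and 5.3), and section 7.1.3 looks at later years. From the assumed June 2018 launch, 43 months × 40 = 1,720 strokes, close to 1,800, with binomial power of 93.1%. What stands is that the end of the post-period is never stated, so the two figures are not reconciled.

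Finally, one might argue that an autocorrelation of 0.3 forces the SD up to at least 2.32/√0.7 = 2.77 and so caps the effect size at 2.1/2.77 = 0.76. That treats a minimum of 480 strokes per year as exact, and assumes that 0.3 describes the observed series with its binomial noise. The plan says neither. Only the narrower finding holds: 2.1 is below binomial noise at the plan's own monthly count.

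**Conclusion.** The concern holds as a mismatch between the power calculation and the specified model, not as an arithmetic error. Over 90% is correct for the unadjusted comparison on 1,440 and 1,800 strokes. With the month term, power for a doubling is about 46% on those counts, about 68-70% on the full ischemic series, and 32% in the short-series case. The 32% needs a 3-year baseline and a 24-month post-period together, so it is a lower bound among the cases examined and not the expected value. No case with the month term reaches 90%. Section 7.1.3 itself treats powers of 70% and below as too low for hypothesis testing.

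These figures rest on two-sided alpha of 0.05, a linear month term, about 40 to 42 strokes per month, a mid-2018 launch for the long series, and no hospital clustering. Clustering across three hospitals could change them, but the documents give nothing with which to size that effect. The 8,000 does not enter the over-90% figure; it only overstates the reserve.

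**What to change.** In section 7.1.1:
- Keep over 90% only as the power without trend adjustment.
- Beside it, give the power and the odds ratio detectable with 90% power for the model with the month term. State the alpha, launch date, monthly count and treatment of clustering, and recompute with the actual launch date.
- Make the full 2010-2021 ischemic series the primary dataset where available.
- State the end of the post-period, and reconcile 1,800 with the 24-month study duration in section 1.1.
- Replace the 8,000 with the roughly 6,000 eligible ischemic strokes from section 6.2.
- Re-derive the cross-check based on SD 2.1 and effect size 1.0, with its series length and trend term, or delete it.

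The cost is protocol wording and a less favourable stated power. No further data request is needed, since 2010-2021 is already sought.
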